kat

PROTOCOL

VERSION 4 – June 2001

SUMMARY

AIMS

This study addresses questions about four developments in knee replacement surgery:

- Is a metal backing plate for the tibial component of the total knee replacement better than a single high density polyethylene component?
- Is it better to resurface the patella as part of a knee replacement or not?
- Does a polyethylene moving component (bearing) between the tibia and femur have a better outcome than standard designs without a moving bearing?
- Is it better to replace a single component of the knee or to replace the whole knee joint?

The assessment of outcome for each of the comparisons is based on:

- Patient-assessed function and health status
- Reoperation rates
- The 'worth' of any additional cost to the NHS

BRIEF OUTLINE OF THE STUDY

Surgeon participants

Surgeons may opt to take part in any (or all) of the comparisons for which they have no clear preference for one of the options.

Patient eligibility

Any patient who requires a knee replacement, and who the surgeon feels would be eligible for the trial.

Information and randomisation

Individual patients will be entered into no more than two possible permutations of the study. Prior to admission to hospital, patients will be sent information about the study, inviting them to take part, and describing the possible options for their operation. If they agree to take part, they will be randomised around the time they are admitted to hospital for their operation. Randomisation will be carried out by the central Trial Office.

Data collection

During their hospital admission, standard information will be collected on the patient's operation and recovery, including short-term complications and data relating to their hospital stay.

Three months and annually after their operation, patients will be sent postal questionnaires asking about their general health, their knee function, and their use of the health service, including any re-admissions and revision surgery. Follow-up will continue for up to eleven years after their operation, to ensure that the long-term performance of the knee operation is properly assessed.

Practical arrangements in clinical centres

The trial is designed to limit the extra work for collaborating surgeons to tasks which only they can do. They will take the lead in the study locally, but resources will be available to provide support. The clinical co-ordinating centres are in Dundee (Department of Orthopaedics and Trauma Surgery - [name]) and Oxford (Nuffield Orthopaedics Centre - [name]). Full-time co-ordinating nurses will be based in Dundee and Oxford to provide support for nurses in collaborating centres. The Trial Office within the Health Services Research Unit in Aberdeen will carry out telephone randomisation, patient postal follow-up, data management, processing and analysis.

Authorship

Publications generated from the study will be attributed to the KAT Trial Group, which will consist of all those who have wholeheartedly contributed to the trial.

FIGURE: SUMMARY OF PATIENT PROGRESS IN THE STUDY

Stages in the study	Actions required by:		
	Surgeon	Study Nurse	Aberdeen Trial Office
Patient deemed eligible ↓	Eligibility determined by surgeon		
Patient sent information ↓		Study nurse and Trial office liaise to send information to patient	
Patient agrees to take part, completes initial questionnaire ↓		Nurse consents patient, collects patient information	
Randomisation ↓		Nurse phones Trial Office	Randomisation by Trial Office
Operation and postoperative hospital stay ↓	Minimal operative details collected by surgeon.	Postoperative information collected by nurse	
Follow-up at 3 months ↓			Postal follow-up by Trial Office
Follow-up at 1 year ↓			Postal follow-up by Trial Office
Follow-up annually			Postal follow-up by Trial Office

CONTENTS

	PAGE
1. Outline of the Trial	1
2. Surgeon Eligibility	1
3. Patient Eligibility	1
4. Trial Recruitment	2
5. The Four Comparisons Being Made	3
6. Clinical Management in the Trial	4
7. Outcome Assessment	4
8. Flexibility of Design	5
9. Arrangements in Clinical Centres	5
10. Clinical Co-ordination	6
11. Data Co-ordination	7
12. Statistical and Economic Considerations	7
13. Trial Committees	12
14. Finance	13
15. Satellite Studies	13
16. Publication	14

Appendices

1. Letter of invitation to patients
2. Patient information leaflets
3. Letter and information sheet for general practitioners
Follow-up letter to GP telling of patient's participation
Alternative Follow-up letter to GP
4. Consent form
5. Participant questionnaires
6. Surgeon's Form, Hospital Care Form and Participant Details Form
7. Authorship policy

This protocol describes a major UK-wide randomised trial to measure the clinical and cost effectiveness of different types of knee replacement. The trial is designed to be as simple as possible for participants and collaborating orthopaedic surgeons. Funds have been provided by the NHS R&D Health Technology Assessment Programme and include resources for both local co-ordination in trial centres and long-term follow-up.

1. OUTLINE OF THE TRIAL

The trial is evaluating four aspects of knee replacements:

- A. Metal backing of the tibial component compared with a single high density polyethylene component.
- B. Patellar resurfacing compared with no resurfacing.
- C. A polyethylene mobile bearing component between the tibia and femur compared with a fixed bearing arthroplasty.
- D. Uni-compartmental arthroplasty compared with total knee replacement.

Individual patients can participate in a maximum of two comparisons and then only if the surgeon responsible for care is substantially uncertain about these particular aspects.

2. SURGEON ELIGIBILITY

Any consultant orthopaedic surgeon may take part provided he or she:

- a. undertakes knee replacements routinely.
- b. is prepared to allow the choice between the specific options in at least one of the four comparisons to be decided by random allocation. (This recognises that surgeons will vary in the comparisons for which they will accept random allocation; during the trial collaborating surgeons will choose which (or all) of the four comparisons they will recruit to - see below.)

3. PATIENT ELIGIBILITY

A patient under the care of a collaborating surgeon will be eligible if:

- a. a decision has been made to have primary knee replacement surgery.
- b. the surgeon has no clear preference for a specific option in at least one of the comparisons. (A patient is therefore not eligible for a trial comparison if the surgeon considers that a particular type of operation is clearly indicated; an example is those patients requiring a highly constrained knee replacement to replace function of the collateral ligaments.)

It is recognised that eligibility will depend on patients' differing functional requirements which are influenced by their age. Although there will not be formal age differentiation in the trial as some people are chronologically older than their function and vice versa, the results of fixed bearing knees in terms of patient satisfaction and longevity of implant (Knutson, 1992) would strongly support the view that until better established the mobile bearing arthroplasty should be reserved for younger patients. It is amongst these patients that the undoubtedly higher technical demands of the operation which increase the risk can be matched by aspirations to increased benefit. It is therefore expected that surgeons will be more prepared to randomise younger patients to this comparison.

4. TRIAL RECRUITMENT

Potential participants will be sent information about the trial comparisons in which the surgeon responsible for care has agreed to participate. When a formal approach is made to the patient this will be to take part in one or two of comparisons, but not more than two. Exact arrangements for recruitment will depend on local admission procedures but will be based on the following:

Fully informing potential participants about the trial

Information about the trial will be given in two stages. A letter of invitation together with information about the parts of the trial in which the surgeon has agreed to participate will be sent to potential participants at home (Appendices 1 and 2). Information will also be sent to their general practitioners in case they are consulted (Appendix 3). More detailed information concentrating on the options for which the patient is eligible will be given to potential participants during discussion with a surgeon or research nurse at a pre-assessment clinic or when admitted before surgery.

Consent to participate in the trial

All eligible patients who agree to participate will sign a trial consent form (Appendix 4). On this, they will confirm that they have been given the information they require and that the study has been explained to them. They will also confirm that they understand that they will be sent a questionnaire from the Trial Office each year.

Formal trial entry and random allocation

Participants will be formally entered into the trial by telephoning an automated service within the Trials Office in Aberdeen. At this phone call, basic descriptive information is given first (hospital; surgeon; patient's name; sex and date of birth) followed by information on the American Knee Society Grade (unilateral, bilateral, generalised arthritis) and the comparison(s) (i.e. A, B, C, or D - see Sections 1 and 5) to which the participant will be recruited. Once these details have all been supplied, the random allocation will be given in return. The allocation will be stratified by the surgeon, with minimisation according to the patient's age, sex, American Knee Society Grade, and whether or not in another randomised comparison. After this phone call the participant is considered irrevocably in the trial for the purposes of the research, irrespective of what happens subsequently. Recruitment will be on the day before surgery (or sooner) to allow theatre staff to prepare appropriate equipment and prostheses. Patients in the fourth comparison (uni-compartmental compared with total) will not be eligible for any of the other comparisons. Each patient can only be entered into the trial once. In the event of a patient being admitted for bilateral knee replacements, the knee indicated by the patient to be the most painful is the knee that should be considered for randomisation.

5. THE FOUR COMPARISONS BEING MADE

The trial comparisons are outlined in Section 1.

In comparison A, the prosthesis used would be the same in every aspect of design other than the tibial component which would be metal backed or not depending on the trial allocation. This option is generally available amongst systems of knee replacement.

Comparison B is straightforward clinically in that surgeons can opt to replace the patella or not irrespective of the design of the prosthesis used.

In respect of comparison C, there may be more variation in the choice between fixed bearing and mobile bearing prostheses. Essentially, the surgeon will choose the metal backed cruciate retaining or substituting design that he or she uses routinely. This will be compared with a mobile bearing design, which preferably but not essentially should be similar in design and make to the surgeon's usual choice of fixed bearing prosthesis.

Comparison D is somewhat different to the other three comparisons. In this, surgeons will use their normal fixed bearing knee or their normal uni-compartmental knee.

6. CLINICAL MANAGEMENT IN THE TRIAL

The surgeon performing the operation will be expected to follow the trial allocation. However, if in the opinion of the surgeon, a clear indication arises for a different operative approach, this should be used and the reason specified.

All other factors will be kept similar if possible, and the surgeon will therefore usually use one manufacturer's range of total knee replacement (see section 5 above).

All other aspects of care, such as deep vein thrombosis prophylaxis, antibiotic prophylaxis, post-operative length of stay and post-operative rehabilitation, are left to the discretion of the surgeon responsible for care.

7. OUTCOME ASSESSMENT

Participation does not require any special tests or extra hospital visits (over and above standard care).

Most data describing outcomes will be collected directly from participants through postal questionnaires. The same questionnaire will be completed at three months and then annually (Appendix 5). It will include:

- the Oxford Knee Score (a twelve-item instrument measuring patients' perceptions of pain and function).
- the SF-12 (an abbreviated form of the SF-36, explaining more than 90% of the variance of the SF36).
- the EQ-5D (to derive quality-adjusted life years, QALYs).
- questions about any further hospital admissions and surgery.

Clinical data will be collected in a standardised way from casenotes to describe operative complications, and any further surgery, especially for revision.

Participants will be flagged at the Office for National Statistics for notification of death registration (and possible later tracing if contact has been lost during follow-up).

Follow-up is planned for at least ten years.

8. FLEXIBILITY OF THE DESIGN TO SUIT ALL COLLABORATING SURGEONS

Individual patients can be recruited to either one or two of the comparisons. The study design is therefore a partial factorial randomised controlled trial.

Individual surgeons will choose to which of the comparisons they will recruit patients. It is unlikely that any surgeon will recruit to all four comparisons. The local trial will therefore be limited to those comparisons that a collaborating surgeon has decided to contribute to. The trial will be described to colleagues and potential participants in these terms.

A good example of the whole process may be: -

[name] agrees to collaborate in the trial but only feels happy using total condylar knee replacements. He prefers cruciate substituting designs but is ambivalent about metal backing and is uncertain about patellar replacement. He therefore contracts to follow the trial allocation for metal or non-metal backing prosthesis plus or minus a patella i.e. two randomised comparisons. Information given to [name] patients will be related to these two comparisons only. [name] will decide whether a particular patient is eligible for one, the other, or both these comparisons, and will then seek informed consent accordingly.

9. ARRANGEMENTS IN CLINICAL CENTRES

The role of collaborating surgeons

The trial is designed to limit the extra work for collaborating surgeons to tasks which only they can do. Study nurses will facilitate the trial locally (see below), and the central organisation will take responsibility for data management and patient follow-up.

Collaborating surgeons will:

- a. establish the trial locally (for example by getting agreement from clinical colleagues, facilitating local research ethics committee approval, identifying and appointing a local study nurse, liaising with the local R&D manager, and ensuring that all clinical staff involved in the care of patients having knee replacement surgery are informed about the trial).
- b. take responsibility for clinical aspects of the trial locally.
- c. notify the Trial Office of any unexpected clinical event which might be related to trial participation.
- d. provide support and supervision for all aspects of the work of the local study nurse.
- e. represent the centre at KAT collaborators meetings.

The role of study nurses

Each clinical centre will have a part-time study nurse, physiotherapist or other equivalent form of staff, whose number of sessions of employment will depend on the number of patients being recruited in a centre. Their responsibilities will be to:

- a. keep local staff informed about the trial and its progress.
- b. keep regular contact with the local surgeon(s).
- c. maintain regular contact with one of the co-ordinating nurses (see below).
- d. identify all those having knee replacement surgery in advance of their admission, and keep a log of whether or not they were recruited to the trial (with reasons for non-participation).
- e. arrange for the initial letter of invitation and information leaflet to be sent to potential participants and to their GPs.
- f. assist the surgeon (for example at a pre-assessment clinic) to give additional information and seek consent to trial entry.
- g. ensure that arrangements are in place for formal trial entry and random allocation, once a participant is admitted for surgery.
- h. arrange for the GP to be informed about recruitment.
- i. ensure that the initial data form describing the index hospital admission is completed promptly and sent to the Trial Office.
- j. collect data describing complications and subsequent admissions to hospital.
- k. facilitate later follow-up, by for example helping with local tracing.
- l. assist in the conduct of satellite studies, if applicable.
- m. provide support for participants in other ways if there are difficulties.
- n. represent the centre at study nurse meetings.

10. CLINICAL CO-ORDINATION

The clinical co-ordinating centres are in Dundee (Department of Orthopaedics and Trauma Surgery - [name]) and Oxford (Nuffield Orthopaedics Centre - [name]). At the start of the trial, representatives from these centres will visit all surgeons expressing an interest in collaborating, aiming to get a commitment from collaborating surgeons to recruit to specified comparisons.

Full-time co-ordinating nurses will be based in Dundee and Oxford. They will:

- a. support the study nurses in collaborating centres.
- b. at the start, help to appoint and train study nurses.

- c. act as a first point of enquiry about any clinical aspect of the trial.
- d. help the Trial Office to ensure complete data collection (through study nurses) during the initial hospital stay, and following any later hospital admission.
- e. act as an intermediary between the Trial Office in Aberdeen and study nurses, and have weekly contact with the Trial Office.
- f. help the Trial Office in connection with any difficulties with later patient follow-up.
- g. act as local study nurses in Dundee and Oxford.

11. DATA CO-ORDINATION

Telephone randomisation and data collection, processing and analysis will be the responsibility of the Trial Office within the Health Services Research Unit in Aberdeen. Staff there will:

- a. facilitate the sending of information to patients and GPs from study nurses.
- b. provide an automated telephone randomisation service for formal trial entry.
- c. monitor collection of in-hospital data and process them, and seek missing or uncertain data.
- d. post our personalised follow-up forms to all participants (at three months and then annually), maximising response by reminders and phone calls, and process returned forms.
- e. ensure the confidentiality and security of all trial forms and data.
- f. conduct extensive data checking and cleaning.
- g. perform interim and main analyses.

12. STATISTICAL AND ECONOMIC CONSIDERATIONS

Sample sizes sought in the four randomised comparisons

The sample sizes sought for the four comparisons have been based on a number of considerations. They have drawn on the relationship between changes in the OKS and other well known outcome instruments, and what previous research has suggested is plausible. They have also taken account of clinical issues, such as the size of differences that seem likely judged on current experience, the possibility of adverse effects, and cost differences.

The table describes the statistical power to detect differences of 1.5, 3.0 and 4.5 in the mean OKS for three sample sizes (700, 350, and 175 in each group), firstly with an alpha error of $2P < 0.01$ and secondly for an alpha error of $2P < 0.05$. These calculations assume a standard deviation for the OKS of 10 points.

Table 3 Statistical power to identify differences of 1.5, 3.0 and 4.5 in mean OKS for three sample sizes, at two levels of statistical significance.

Mean difference in OKS	1.5		3.0		4.5		
	2P<0.01	2P<0.05	2P<0.01	2P<0.05	2P<0.01	2P<0.05	
Number in	700	60	80	>99	>99	>99	>99
each randomised	350	<50	50	91	97	99	>99
group	175	<50	<50	60	80	94	98

Although the OKS is the principal outcome, possible differential effects on revision rates have also been considered where appropriate. Although these are presented here as simple rate differences, these analyses will in fact be able to identify smaller differences with the same statistical power as that indicated. There are two reasons. First, these analyses will be based on the time to revision using prosthesis 'survival curves' rather than a simple dichotomous variable. Second, survival curves will also be generated for a composite outcome which includes patients whose knee prostheses are judged (by falling below a predefined threshold on the Oxford score) to have failed, in addition to those who actually had revision (thus increasing the number of 'events', and hence statistical power).

(i) Metal backing of tibial component

The concern in this comparison is that loosening of non-metal backed tibial components may lead to severe symptoms in the long-term. The aim therefore is for a sample size which is large enough to identify a difference equivalent to a typical category change in the American Knee Society Score (that is, a difference of about 3.0 in the OKS). This will require a minimum of 175 per group to have reasonable power (80%) with an alpha error of 2P<0.05 (see Table). A comparison with 235 in each group, for example, would have 90% power to identify this difference.

(ii) Patellar resurfacing

Based on preliminary results of follow-up of a small randomised trial - currently unpublished - comparing patellar resurfacing with no resurfacing, the effect of resurfacing, if it exists, is likely to be relatively small and near a difference in the mean OKS of 1.5. The table shows that a trial with 700 in each group would have 80% power to identify this difference (2P<0.05). A trial of this size (about 1500 people) would also have reasonable

power to identify differences in revision rates over prolonged follow-up - more than 90% power to detect a halving from 10% to 5%, for example.

(iii) Uni-compartmental arthroplasty

A non-randomised comparison of two cohorts characterised by management with either a uni-compartmental prosthesis or total knee replacement showed a difference in the mean OKS scores of 3.4, whereas follow-up of similar but smaller randomised cohorts suggested a smaller difference of 1.6, albeit with a wide confidence interval. The aim is therefore for a trial with at least 175 participants in each group, so that there is a good chance of identifying a difference in the mean OKS of 3.0. There may be higher revision rates after uni-compartmental arthroplasty. A trial of this size would have 90% power to identify an increase from 5% to 15% in this respect.

(iv) Mobile versus fixed bearing arthroplasty

The substantially greater costs of mobile bearing prostheses can only be justified if there are clear benefits. The aim is to identify benefits equivalent to an increase in the OKS of 3.0 or greater. A trial with 350 in each group (see Table) has over 90% power to identify this at the 1% level of significance and 97% power to show a significant difference at the 5% level. There are concerns about possible short-term failures, such as dislocation or related mechanical problems, associated with the mobile bearing arthroplasty. If 1% such complications are expected in the fixed bearing group, a trial with 350 in each group has about 90% power to identify an increase to 5%.

Other details of the analysis plan

All analyses will be based on 'intention to treat' and no participant with data will be excluded. The principal comparisons will be between:

- a. all those allocated a metal backed tibial component compared with all those allocated a single component.
- b. all those allocated patellar resurfacing compared with all those allocated no resurfacing.
- c. all those allocated mobile bearing compared with all those allocated fixed bearing.
- d. all those allocated uni-compartmental arthroplasty compared with all those allocated total knee replacement.

These main analyses will measure the ‘main effects’ of the alternative approaches. The partial factorial design will, however, provide an opportunity to assess whether there is any interaction between patellar resurfacing and the other comparisons (that is, whether a combination has any greater or lesser effect than would be expected from the main effects).

Differences between the groups in revision rates might bias comparisons of the Oxford scores. For this reason these analyses will be run in two ways: firstly on the actual scores at a particular time, irrespective of further surgery (aiming to compare the clinical policies actually used, including repeat surgery); and second, after imputing a score for those who had revision surgery (aiming to compare the initial surgery used in the trial). Although patient survival will be a measure of outcome and described in trial reports, most analyses will be based on the assumption that the alternative prostheses do not have differential effects on mortality. Analyses of the Oxford score will principally be based on survivors but possible effects of excluding those who died will be explored using imputed scores based on the data available. In respect of the revision analyses, participants will be assumed to be at risk only when alive, using a multi-decrement life table approach. It is difficult to predict the proportion of participants who will die or be lost to follow-up, but allowance has been made by aiming to recruit at least 1500, 750 and 400 as applicable.

Additional analyses, stratified by surgeon, will explore any effects of make of prosthesis, surgical experience (‘the learning curve’) and rehabilitation policy.

Timing and frequency of analyses and reporting

Two principal analyses are planned - at six years and then at twelve years.

By six years, participants will have had a median of four years follow-up (assuming it takes six months to initiate the trial, two years to recruit all patients, and six months to complete and report analyses). By this stage, data on early complications, which are likely to be mainly medical, will be available. There will be some early failures, for example due to infection. Outright device failure will be uncommon, but differences in functional scoring could be apparent.

By twelve years, follow-up will have been for a median of ten years. A substantially larger number of device failures and subsequent revisions will have occurred by then.

Confidential interim analyses will be performed at other times as requested by the Data Monitoring Committee, which is expected to meet at least annually (see below).

Economic evaluation

The type of economic analysis performed for each comparison will depend on the findings. If there are no differences in outcome for a particular comparison, cost minimisation analysis will be used. If differences emerge, cost-effectiveness analyses from a societal perspective will be performed. The primary measure of effectiveness will be pain and function as assessed by the Oxford Knee Score. Information on utilities will also be available for analysis because trial patients will also complete EQ-5D for which population-weighted values are available.

Costs of alternative forms of knee-replacement surgery may be considered as either short term or long term. In the short term, differences in costs of alternatives will arise from differences in surgical procedure, technology, forms of care during hospital stay, length of hospital stay and short-term complications (wound infection, deep vein thrombosis, pulmonary embolism). In the long term, major differences in costs of the surgical alternatives will arise in relation to differences in longer term outcomes, particularly recurrence of pain and physical dysfunction requiring further primary, community and hospital care, and, in some cases, need to revise surgery.

Three data gathering components will be used to address these major sources of variation in costs (i) early (ii) medium to long term and (iii) modelling.

(i) Early data collection

Cost generating events in the short term will be recorded by means of a patient-specific checklist administered by research nurses at the participating hospitals, using theatre records and hospital notes. This will cover time in theatre and on ward, surgical procedure(s), diagnostic and investigative procedures and tests, and duration and intensity of rehabilitation.

(ii) Medium to long-term data collection

Following initial hospitalisation, information on health care resources used will be recorded using questions integrated into the main follow-up questionnaire administered to all patients annually. This will estimate annual numbers of knee-related primary care

consultations, out-patient visits, and use of other health care services. Full information on all subsequent in-patient admissions for investigative procedures or revision surgery will be recorded using the research nurse system described elsewhere in this protocol.

(iii) Modelling

Primary economic analysis will use the resource volumes and rates of revision surgery recorded during the follow-up period. However, in order to extend the economic analysis beyond the follow-up period, some modelling will be performed, using trial data on observed revision rates, resource use and risk factors to set parameter values. Uncertainty surrounding the model results will be formally reported.

Unit costs for all cost generating resource events recorded above will be obtained from participating centres and from national data sets.

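### Protocol Section 12 promises, without condition, that the revision analyses will detect smaller differences than its power figures show; neither of its two reasons supports that promise as written

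*Protocol*

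**What the plan says.** Protocol Section 12, under the heading on sample sizes, names the OKS as the principal outcome and says that revision rates were considered where appropriate. It presents them as simple rate differences and adds that "these analyses will in fact be able to identify smaller differences with the same statistical power as that indicated". Two reasons follow.

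- Reason 1: "these analyses will be based on the time to revision using prosthesis 'survival curves' rather than a simple dichotomous variable".
- Reason 2: "survival curves will also be generated for a composite outcome" made up of revision plus knees judged to have failed on an OKS threshold, "thus increasing the number of 'events', and hence statistical power".

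The figures to which this applies are:

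- Patellar resurfacing (B): 700 per group, 10% v 5%, more than 90% power.
- Uni-compartmental arthroplasty (D): at least 175 per group; such a trial "would have 90% power to identify an increase from 5% to 15" per cent.
- Mobile bearing (C): 350 per group, 1% v 5%, about 90% power. This concerns short-term failures rather than revision as such.

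Under the further details of the analysis plan, "participants will be assumed to be at risk only when alive". Death and loss are called hard to predict, and at least 1500, 750 and 400 are to be recruited as an allowance. That is 750 (B), 375 (C) and 200 (D) per group.

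**The concern.** The promise carries no condition, so a reader will take the quoted revision powers as understated and the composite as the more sensitive analysis.

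Timing adds information beyond a count of events mainly when events are common or follow-up differs between patients. Neither applies to no-loss figures at 1–15% incidence. Adding events to an endpoint helps only if treatment moves those events too; low scores that arise equally in both arms dilute the contrast.

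At stake is how the results are read. A composite with no difference could be taken as reassurance about revision because the protocol has described it as the stronger test.

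**Working it through.** **Inputs.** Rates and group sizes are as above, with recruitment targets of 750 (B), 375 (C) and 200 (D) per group. The rate figures state no alpha; I assume two-sided 5%, the level Section 12 uses elsewhere. The documents give neither the ten-year death or loss rate nor the OKS-failure rate q, so both are varied.

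**1. Reproduce the stated powers.** Arcsine formula: h = |2·arcsin√p1 − 2·arcsin√p2|, power = Φ(h√(n/2) − 1.96).

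- B: 0.1925 × √350 = 3.601, power 95.0%.
- D: 0.3444 × √87.5 = 3.221, power 89.6%.
- C: 0.2507 × √175 = 3.316, power 91.3%.

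All three reproduce. The pooled normal formula gives 94.5%, 88.0% and 87.5%.

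**2. Reason 1, no loss.** Exponential times were matched to the stated risks, with 20,000 simulated trials for each comparison. The hazard ratio is ln(1−p2)/ln(1−p1) and expected events are n(p1+p2).

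| | Hazard ratio | Events | Log-rank | Chi-squared |
|---|---|---|---|---|
| B, 700 per group | 0.49 | 105 | 94.7% | 94.8% |
| D, 175 per group | 3.17 | 35 | 89.2% | 89.0% |
| C, 350 per group | 5.10 | 21 | 90.9% | 90.8% |

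There is no gain. The Schoenfeld formula, Φ(½√events·|ln HR| − 1.96), suggests one (95.8%, 92.7%, 96.2%), but simulation shows that it overstates power at hazard ratios this extreme with so few events. The Freedman formula, Φ(√events·|1−HR|/(1+HR) − 1.96), gives 94.3%, 86.8% and 86.9%.

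**3. Death and loss.** Simulated log-rank power with censoring independent of arm (simulation error about half a point):

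| Assumed ten-year loss | B, 750 per group | D, 200 per group |
|---|---|---|
| 20% in total | 94.1% | 90.0% |
| 40% in total | 90.9% | 87.1% |
| death 20%, other loss 10% | about 94% | about 89% |
| death 30%, other loss 15% | about 91% | about 86% |
| death 40%, other loss 20% | about 88% | about 82% |

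At 700 and 175 per group, without the allowance, 20% total loss gives 92.6% and 85.9%; 40% gives 88.8% and 81.3%.

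**4. Reason 2.** Composite risk is 1 − (1−p)(1−q).

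*OKS failures unrelated to implant, q = 10%.*

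- B: 1 − 0.90×0.90 = 19.0% against 1 − 0.95×0.90 = 14.5%. The hazard ratio is 0.743 with 700×0.335 = 234.5 events. Schoenfeld: ½√234.5 × 0.2965 − 1.96 = 0.31, power 62%.
- D: 14.5% against 23.5%. The hazard ratio is 1.71 with 66.5 events; power is 59% (57% by the pooled two-proportion formula).
- At q = 20%, power is about 40% (B) and 38–39% (D).

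*OKS failures with the revision hazard ratio.* Here q applies to the 10% arm in B and the 5% arm in D. At q = 10%, B compares 19.0% with 1 − 0.95×0.90^0.487 = 9.75%, and D compares 14.5% with 39.1%. Power exceeds 99% in both, and is at least 99% from q = 5%.

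*Break-even at q = 10%.* Composite power equals revision-alone power (both by Schoenfeld) when the hazard ratio among OKS failures is about 0.73 for B and 1.71 for D. Effects stronger than these gain power; weaker ones lose it. That 1.71 also appears above as D's diluted composite hazard ratio is coincidence.

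*The protocol's own OKS effect for B.* A difference of 1.5 points on an SD of 10 is 0.15 SD. Assume normal scores and an effect favouring the arm with fewer revisions. At q = 10% the better arm has Φ(−1.282 − 0.15) = 7.6% failures, so the composite is 19.0% v 12.2%. Pooled power is 93.8%, against 94.5% for revision alone. At q = 5%, 20% and 30% it is 94.5%, 92.3% and 90.8%. Even this favourable case yields no gain.

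**The case against.** Four points on the other side have force.

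- **The recruitment allowance.** A reader might infer from the at-risk-only-while-alive rule that the revision powers are optimistic. The documents do not support that. The targets of 750 and 200 per group offset roughly 20% total loss, and whether ten-year loss exceeds that cannot be settled from the protocol.
- **The comparator for reason 1.** The protocol does not define its simple dichotomous analysis. If that analysis kept only people followed throughout, its approximate power at 175 per group under the three death/loss pairs would be 76%, 67% and 58%, against 84%, 81% and 77% for log-rank. Survival analysis then helps. But this recovers part of what loss takes away; it does not improve on the quoted no-loss figures. If known revisions are kept in the simple analysis, the tests differ by at most about 1.3 points with up to 40% loss.
- **Reason 2 is not simply wrong.** The trial expects implants to affect the OKS, and the protocol links tibial loosening to severe symptoms, so a null effect on OKS failure is not the natural default. An effect that carries over fully raises power to at least 99%.
- **The composite is an extra analysis.** A reader might infer that it weakens or hides a revision difference. It cannot, because time to revision is analysed in its own right.

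Revision is also not the principal outcome. These points limit the concern, but none restores the unconditional promise.

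**Conclusion.** The promise of smaller detectable differences should not stand as written. With complete follow-up, time-to-event analysis gives essentially the power of comparing proportions. The claim that more events mean more power holds only under a condition that the protocol does not state: at 10% OKS failure, a hazard ratio among those failures of about 0.73 or lower (B) or 1.71 or higher (D). The range runs from 62% (B) and 57–59% (D) with no effect on OKS failure to at least 99% with the full revision effect.

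The revision powers themselves reproduce. They are no-loss figures, holding at about 90% or more at the recruitment targets up to about 20% total loss. With assumed death/loss of 30/15% to 40/20%, B falls to about 91–88% and D to about 86–82%. They are therefore not shown to be conservative, and not shown to be overstated either.

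This rests on constant hazards, two-sided 5% tests, censoring independent of arm, and assumed ranges for loss and OKS failure. No sample size changes; the point is a modest one about a stated property that the design does not have.

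**What to change.** In Protocol Section 12:

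1. Delete the sentence promising smaller detectable differences, together with the survival-curve reason. If a reason for time-to-event analysis is wanted, give its handling of deaths and losses.
2. Make any claimed gain from the composite conditional on a stated effect among OKS failures.
3. Label the revision powers as no-loss figures, and show them over a range of death and loss at the recruitment targets.
4. Keep time to revision as its own analysis, and report the composite with its revision and OKS components shown separately.

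The cost is protocol wording and a small table. The stated revision power will look slightly less favourable; recruitment, data collection and the principal analysis are unaffected.
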